The current proposal will build on our pilot study and utilize a double-blind, mixed-model design with a between-groups factor of dose (pioglitazone vs. placebo) and a within-subjects factor of time. Eligible participants will consist of treatment-seeking individuals with AUD who score high on screening measures of stress/anxiety and stress-related drinking. Study medication (pioglitazone or placebo) will be administered for 8 weeks. Relapse risk outcomes will be assessed using both a human laboratory paradigm of stress reactivity and stress-induced craving (Specific Aim 1) and real-life measures of stress/anxiety, craving, and alcohol consumption (Specific Aim 2).

Strengths of the current proposal include: 1) targeting individuals with elevated stress/anxiety and AUD; 2) biological assessment of stress reactivity (heart rate, blood pressure, salivary cortisol); 3) a multi-dimensional assessment of alcohol craving incorporating relatively novel behavioral economic measures (i.e., alcohol demand, delay discounting); and 4) inclusion of powerful Bayesian statistical tools that are well suited for smaller samples, such as the current proposal.

We propose the following Specific Aims:

Specific Aim 1: To examine the effects of pioglitazone on stress-induced relapse risk in a laboratory model.

Hypothesis 1a: Participants receiving pioglitazone will show decreased stress reactivity (heart rate, blood pressure, salivary cortisol) compared to those receiving placebo.

Hypothesis 1b: Participants receiving pioglitazone will show decreased alcohol craving (subjective, alcohol demand) compared to those receiving placebo.

Specific Aim 2: To examine the effects of pioglitazone on drinking, stress/anxiety, and alcohol craving in the natural environment.

Hypothesis 2a: Participants receiving pioglitazone will show greater reductions in weekly psychometric measures of stress/anxiety compared to those receiving placebo.

Hypothesis 2b: Participants receiving pioglitazone will show greater reductions in weekly psychometric measures of alcohol craving compared to those receiving placebo.

Hypothesis 2c: Participants receiving pioglitazone will show greater reductions in past week alcohol use (heavy drinking days, average drinks/day) compared to those receiving placebo.

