Figure 1. Changes in stress reactivity (left panel) and weekly measures of stress/anxiety, alcohol craving, depressive symptoms, and alcohol consumption (right panel).

Overall Study Design. To accomplish the project aims, we will utilize a double-blind, mixed-model design with a between-groups factor of dose (pioglitazone vs. placebo) and a within-subjects factor of time. We will utilize urn-randomization based on gender and severity of alcohol use (AUDIT). A summary of the study timeline, procedures, and assessments is shown in **Table 1** below.

Table 1. Outline of Study Timeline, Procedures, and Assessments

Study Week	0	1	2	3	4	5	6	7	8
Procedures and Assessments	IRB	NU	BE						
Consent and Baseline Screening	IRB	APP	OVAL						

SCID, ASI, KMSK, TLFB, CIWAA, AUDIT	X								
Receive Study Medication (Pioglitazone or Placebo)	X	X	X	X	X	X	X	X	X
Assess Medication Compliance and Adverse Events		X	X	X	X	X	X	X	X
Brief Counseling	X	X	X	X	X	X	X	X	X
Human Laboratory Assessments (Specific Aim 1)									
Stress-Reactivity Assessment (Salivary Cortisol, HR, BP, self-report)	X				X				X
Alcohol craving (self-report, brief alcohol demand)	X				X				X
Weekly Assessments (Specific Aim 2)									
Alcohol Use and Craving (TLFB, BrAC, ETG, PACS, DMQ-R)	X	X	X	X	X	X	X	X	X
Stress and Anxiety (HAM-A, PSS, PCL-5)	X	X	X	X	X	X	X	X	X
Delay Discounting, Alcohol Demand (purchasing task)	X				X		X	X	X

SCID - Structured Clinical Interview for DSM-5, **ASI** - Addiction Severity Index⁶⁵; **KMSK** - Kreek-McHugh-Schluger-Kellogg scale⁶⁶; **TLFB** - Timeline Followback⁶⁷; **CIWAA** - Clinical Institute Withdrawal Assessment for Alcohol⁶⁸; **AUDIT** – Alcohol Use Identification Test⁶⁹; **BrAC** – Breath Alcohol Concentration; **ETG** – Ethyl Glucuronide; **PACS** – Pennsylvania Alcohol Craving Scale⁷⁰; **DMQ-R** – Drinking Motives Questionnaire Revised^{1,2}. **HR** – Heart Rate; **BP** – Blood Pressure; **HAM-A** – Hamilton Anxiety Rating Scale⁷¹; **PSS** – Perceived Stress Scale⁷²; **PCL-5** - PTSD Checklist for DSM-5⁷³.

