One week's supply of the study medication will be dispensed. Cell-phone assisted remote observation of medication adherence (CAROMA) will be used to assess compliance. Riboflavin will be added to medication capsules and urine ultraviolet fluorescent tests will be conducted at weekly clinic visits to also assess compliance. Participants will receive \$10 at each clinic visit based on self-report, CAROMA, and riboflavin measures all being consistent with medication compliance. For safety purposes, blood will be drawn every 2 weeks for liver function testing as is standard for other Pioglitazone protocols at the CNRA.

Assessment of Stress Reactivity. At baseline and Weeks 4 and 8, stress reactivity will be assessed using a modified cold-pressor task (CPT). The CPT is widely used as a stress-inducer in human laboratory studies and elicits moderate activation of the sympathetic nervous system and limited activation of the HPA-axis, which are two major stress systems in the body⁹⁸⁻¹⁰¹. HPA-axis activation during the CPT can be increased by incorporating a social evaluative component. These will include 1) a study member dressed in a white labcoat and taking notes on a clipboard; and 2) a webcam and monitor showing the participant's face. Participants will be informed that their facial expressions will be assessed during the CPT. The addition of these social components during the CPT has been demonstrated to selectively activate the HPA-axis and significantly increase salivary cortisol levels¹⁰⁰. During the CPT, participants will submerge their dominant arm in an ice-water bath for up to 2 minutes. Physiological measures of stress reactivity will include HR, BP, and salivary cortisol consistent with previous studies from our group^{102,103}. HR and BP will be will be assessed using standard laboratory equipment. Saliva samples will be collected in swabs using the Cortisol-Salivette[®] system (Sarstedt) and measured using the Cortisol ELISA Kit (Enzo Life Sciences), per manufacture instructions, detailed in Suchting et al (2019)⁴. Alcohol craving will be assessed using a 4-item questionnaire⁷⁵ as well as the BAAD. Stress will be assessed using a single-item VAS question.

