Brief Counseling. At baseline, all participants will receive the NIAAA booklet "Rethinking Drinking: Alcohol and Your Health" providing research-based information related to alcohol use (RethinkingDrinking.niaaa.nih.gov). Study therapists will go over the booklet with the participant at the initial visit and at subsequent weekly visits using motivational interviewing techniques. At each visit, participants will also be assessed for recent alcohol use (self-report, ETG, BrAC), alcohol craving (PACS), and stress/anxiety (HAM-A, PSS). At the end of the study, referrals to local alcohol treatment services will be provided as needed.

Participant Payment & Compensation. Participants will receive \$50 for completing the baseline screening, \$25/visit for attending study visits (9 visits), \$25/assessment for completing stress reactivity

Table 2. Time Course for Assessing Stress-Induced Relapse Risk

Time (pm)	Study Procedures
3:00	Assess Craving, BAAD, Stress, Cortisol, HR, BP
3:15	Cold Pressor Task
3:20	Assess Craving, BAAD, Stress, HR, BP
3:45	Assess Craving, BAAD, Stress, Cortisol, HR, BP

assessments (3 assessments), \$10/week for medication compliance (8 weeks), and \$100 for completing the study (\$530 total). Participants will also receive \$5 compensation for busfare/parking at each study visit.

DATA ANALYTIC STRATEGY

Descriptive Statistics & Confounding Variables Descriptive statistics will evaluate measures of central tendency (continuous) and frequencies (categorical) for study-related variables. General variable relationships will be evaluated using correlation analyses. Preliminary analyses will inspect relationships between sample characteristics (e.g., demographics), predictor variables (e.g., inflammatory markers), and specified outcome variables (e.g., resilience measures) via traditional statistical tests (e.g., chi-square, Mann-Whitney-Wilcoxon, Kruskal-Wallis, and *t*-tests). Sample characteristic variables demonstrating a relationship with both the predictor and outcome variables in a given model will meet criteria as a potential confounder^{104,105} and included as a covariate in such models for hypothesis testing and explored as potential moderators of treatment group effects on experimental outcomes.

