Participants will be self-referred in response to various study advertisements via newspaper and radio. Individuals who call for information will be given a brief description of the study. Those interested will then be asked to answer questions about their current substance use. A trained research assistant will conduct this telephone-screening interview. Eligible subjects will be scheduled for an in-person intake visit at which time a research staff member will present the informed consent form. The consent form will detail the requirements of study participation (e.g., # of visits, type of data collected, time commitment, etc.).

Subjects will be told that the purpose of the study is to evaluate a medication's effect on their alcohol use in their natural environment and following exposure to an acute stressor. Information about each study procedure will be explained. Subjects will be informed that they will attend weekly clinic sessions and to take their medication. Other information on the consent form will include a full description of study requirements, reimbursement, risks, benefits, alternatives, and the role of the local IRB. All questions will be answered before written consent is requested.

E.2.2. Protection Against Risk

Thorough screening of all subjects including history and physical examination, serum chemistry and hematology, EKG, urinalysis and Urine Drug Screen as well as structured psychiatric interviews will be completed on all subjects. Exclusion criteria include subjects at greatest risk of side effects of pioglitazone, including those with congestive heart failure, significant liver disease, edema, and diabetes, as well as risks of alcohol use (pregnant women). Monitoring of weight to capture potential fluid retention will occur at each visit. Weekly assessment for edema and urine pregnancy will occur. Twice monthly serum chemistry and hematology will take place to monitor liver functions and hemoglobin/hematocrit. In addition twice monthly EKGs will be done. Female subjects must agree to use an effective barrier method of birth control to minimize risk of pregnancy.

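### Table 1 marks drug receipt at nine visits, implying 63 days of supply against a stated 56, and the Week 8 supply, if dispensed, has no scheduled safety check

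*Combined protocol and SAP*

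**What the plan says.** - **Table 1 (Approach, Overall Study Design), titled "Outline of Study Timeline, Procedures, and Assessments".** It has nine columns, Weeks 0 to 8, and none later. The row "Receive Study Medication (Pioglitazone or Placebo" carries a mark in every column. The next row, "Assess Medication Compliance and Adverse Events", is blank at Week 0 and marked at Weeks 1 to 8.
- **Study Medication and Compliance.** "One week's supply of the study medication will be dispensed".
- **Specific Aims.** "Study medication (pioglitazone or placebo) will be administered for 8 weeks". The Introduction to the Revised Proposal also gives the trial duration as 8 weeks.
- **Participant Payment & Compensation.** The payments include $"25/visit for attending study visits (9 visits") and $10 a week "for medication compliance (8 weeks"), within a total of $530.
- **E.1.3 Potential Risks and E.2.2 Protection Against Risk.** Liver tests and EKGs are due every two weeks, and weight is taken at every visit. In addition, "Weekly assessment for edema and urine pregnancy will occur". None of these has its own row in Table 1.
- **Data Safety Monitoring Plan.** This describes general procedures, gives no end date for adverse event reporting, and defers to a more detailed plan that is not part of the documents shown.

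**The concern.** Each compliance and adverse event check looks back over the supply handed out one visit earlier. That is why the row is blank at Week 0 and begins at Week 1. A supply handed out at Week 8 would need a check at Week 9, and the schedule has no Week 9.

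Table 1 is the only visit-by-visit schedule in the documents, so staff who dispense may well work from it. Followed as printed, it would give participants a week of capsules at the last scheduled visit, with nothing scheduled afterwards. The protocol itself names hepatic failure, fluid retention with worsening heart failure, and exposure in pregnancy as risks, and it answers each with repeated monitoring while drug is taken. A dispensed week outside that monitoring would fall short of the protocol's own standard. It would also leave the safety comparison between arms without scheduled data for part of the dispensed exposure.

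**Working it through.** This is a count. No power formula is involved.

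**1. Reproduce the plan's own figure.** The items in Participant Payment & Compensation are $50 for screening, $25 for each of 9 visits, $25 for each of 3 stress assessments, $10 for each of 8 medication weeks, and $100 for completion.

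50 + 25×9 + 25×3 + 10×8 + 100 = 50 + 225 + 75 + 80 + 100 = **$530**, as stated.

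With 9 medication weeks and the other items unchanged, the total would be 530 + 10 = $540. The payment plan therefore has nine visits but eight medication weeks.

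**2. Count the supply in Table 1.** Marks in the medication row: Weeks 0, 1, …, 8 = 9. Supply per dispensing: 7 days.

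- As printed: 9 × 7 = **63 days**.
- Stated duration: 8 × 7 = **56 days**.
- Difference: 63 − 56 = **7 days**, and 7/63 = **11%** of the dispensed supply.

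**3. Match supplies to checks.** Marks in the compliance and adverse event row: Weeks 1 to 8 = 8.

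| Supply given at | Covers | Scheduled check |
|---|---|---|
| Week 0 | days 0–7 | Week 1 |
| … | … | … |
| Week 7 | days 49–56 | Week 8 |
| Week 8 | days 56–63 | none |

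Nine supplies meet eight checks, and the ninth has no partner.

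**4. The other safety checks.** Their timing has to be inferred, because Table 1 does not list them. Counted from Week 0, a two-weekly rule puts liver tests and EKGs at Weeks 2, 4, 6 and 8. Checks made weekly or at every visit also end at Week 8, because no later visit is described. On that inference, days 56 to 63 would have no scheduled weight, oedema, pregnancy, liver or EKG check either.

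**5. What would agree.** Eight supplies give 8 × 7 = 56 days, which matches the stated duration, the eight checks and the eight paid compliance weeks. Nine supplies match none of these three. This shows only where the documents disagree; it does not settle how long drug should be given.

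**The case against.** The strongest reply is that the Week 8 mark is a slip, or that the row loosely means that the participant is on medication at that point. The Introduction to the Revised Proposal, the Specific Aims and the payment section all give 8 weeks. The text introducing Table 1 calls it a summary, and other rows of it conflict with the narrative. Delay discounting and the purchasing task are marked at Weeks 0, 4, 6, 7 and 8, while the behavioral economic section gives baseline and Weeks 4 and 8. The PCL-5 sits in a weekly row, while the text again gives baseline and Weeks 4 and 8. Approval-stamp fragments also run into the table's cells.

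Much of this stands. A reader might infer that participants will take a ninth week of drug after their last safety check. The documents do not establish that: it requires the Week 8 mark to be literal and to override the text elsewhere. A reader might also infer that adverse events arising after Week 8 would go uncollected. That is too strong, because the Data Safety Monitoring Plan sets no end date for reporting, requires immediate reporting of serious events, and defers to a detailed plan not shown. The most the text supports is that no collection is scheduled after Week 8.

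The reply does not remove the contradiction. An extraction fault in this particular row is unlikely: nine marks fill nine columns, as in the counseling row, and the row directly below correctly leaves Week 0 blank. If marks in Table 1 are loose in several places, that is further reason to correct the one that governs the handing out of drug.

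**Conclusion.** The inconsistency is real and can be checked by counting: nine marked dispensings (63 days) against a stated 8 weeks (56 days), eight paid compliance weeks and eight scheduled checks. The excess is 7 days, or 11% of the supply as printed. It would apply to any participant who attends Week 8 and is given drug there.

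The consequence for patients is conditional. It rests on three assumptions: that sites follow the Table 1 mark literally, that each dispensing is one week's supply, and that nothing outside these documents schedules a later contact. The absence of liver, EKG, weight, oedema and pregnancy checks after Week 8 rests further on inferred timing. Extra exposure is therefore a risk of the printed schedule and not a demonstrated fact.

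The point is more than clerical, because it concerns whether drug leaves the clinic at the last scheduled visit, and it should be corrected. It has no bearing on sample size, alpha, power or any efficacy analysis.

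**What to change.** - Reconcile the Table 1 medication row with the Specific Aims, Study Medication and Compliance, and Participant Payment & Compensation. The number of dispensings, the stated treatment duration and the scheduled safety checks should agree, and no dispensed week should lack a scheduled check.
- State the adverse event collection window relative to the last dispensed dose. If the detailed safety monitoring plan already defines it, a cross-reference is enough.

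How long drug is given, and how follow-up after the last dose is managed, remain the sponsor's decisions. The cost is a one-row table correction and one sentence.

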Recruitment. Recruitment strategies will include local advertising in print media, public service announcements on radio, and referrals to CNRA in the Houston metropolitan area. Additionally, we will utilize the University of Houston SONA system, which provides students credit for participating in various research studies. Access to SONA is made possible with the inclusion of [name] (Consultant). We will also recruit from the Department of Psychiatry Recruitment Registry: HSC-MS-23-0768.

Participants. We will enroll 60 participants to reach a target of **N = 50** completers (25/group). Participants will consist of otherwise healthy treatment-seeking individuals with AUD exhibiting elevated baseline stress/anxiety. All participants will meet the following inclusion and exclusion criteria:

Inclusion criteria. Be treatment-seeking individuals diagnosed with AUD (DSM-5); be at least 18 years old and fluent in English; past month excessive alcohol use (>7 drinks/week for woman, >14 drinks/week for men, >3 drinks/occasion for women>4 drinks/occasion for men)³⁵; exhibit baseline measures of either 1) 8-23 on HAM-A indicative of mild to moderate anxiety, 2) 14-26 on PSS Score indicative of moderate stress, or 3) ≥ 2 on DMQ-R questions related to drinking indicating that individuals drink at least “some of the time” to cope; and exhibit increased stress reactivity (increased physiological response and/or self-report) at the baseline stress reactivity assessment.

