HAM-A) compared to those receiving placebo. **Hypothesis 2b:** Participants receiving pioglitazone will show greater reductions in weekly psychometric measures of alcohol craving (primary measures: PACS) compared to those receiving placebo. **Hypothesis 2c:** Participants receiving pioglitazone will show greater reductions in past week alcohol use (primary measures: heavy drinking days as defined by >3 drinks/occasion for women and >4 drinks/occasion for men, average drinks/day) compared to those receiving placebo.

For all hypotheses, GLMM will model primary outcome measures as a function of the main effects and interaction between treatment and time.

Sample Size and Power Considerations

Frequentist Analyses. Power for **Specific Aim 1** is based on the rate at which we may detect the three-way interaction between time, treatment, and CPT measurement point for a given measure of stress reactivity (transformed for normality) across $k = 1000$ Monte Carlo simulations (executed via SAS 9.4). Calculations assume the following conditions: $\alpha = 0.05$, an autocorrelation of $r = 0.50$ between consecutive observations (with a decay of $r = -0.10$ for subsequent observations), and a small correlation of $r = 0.05$ for observations occurring at the same time point across groups. Based on these assumptions, the different sample sizes (pragmatic and pessimistic) stipulated in **Table 3** each provide power to detect small-to-moderate effect sizes (treatment group differences expressed as Cohen's D, with effects unfolding in linear fashion over time). Power for **Specific Aim 2** is based on evaluating reductions in drinks per week. Estimates are derived using G*Power 3.1.9.2. Assuming $\alpha = 0.05$ (two-tailed) and an average baseline of drinks/week across participants (calculated as an average from 14 and 7 drinks/week for a 3:1 ratio of males to females, respectively), the different sample sizes (pragmatic and pessimistic) stipulated in **Table 3** each provide power to detect varying decreases in alcohol consumption.

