Bayesian Analyses. The Bayesian analyses in the current proposal will provide probabilistic estimates of effects for all hypotheses irrespective of statistical power. Moreover, the MCMC approaches utilized in Bayesian analyses do not rely on large sample size assumptions. Bayesian analyses will focus on posterior probabilities ≥ 0.75 (equivalent to a Bayes factor = 0.33 or 3.0) that parameter estimates are greater or less than zero to emphasize the value in discerning model effects.

Table 3. Power estimates for Aims 1 and 2 given different sample and effect sizes.

N (N/group)	SA1: Group Difference (Cohen's D)			SA2: % Decreased Consumption		
	D = 0.50	D = 0.40	D = 0.30	-12.0%	-11.0%	-10.0%
50 (25/25)	100.0%	97.8%	84.6%	97.8%	95.2%	90.8%
40 (20/20)	99.8%	95.0%	71.8%	88.6%	82.5%	74.6%

Cohen's D for observed within-subject effects sizes from our Preliminary Data are as follows: HR (0.8), BP (systolic - 0.5, diastolic - 1.6), cortisol (0.13), PSS (2.1), HAM-A (1.3), BDI (1.2), PACS (1.5), Drinks/week (1.3), Heavy drinking (0.8). Note that Table 3 effect sizes represent between group differences unfolding over time.

STUDY TIMELINE

The time frame illustrated in **Table 4** below is based on conservative estimates. We will continuously monitor our procedures and implement measure to enhance progress as indicated. Our goal is to enroll 60 subjects to achieve 25 completers/group. However, we will continue to enroll subjects based on available resources and subject attrition. Pre-award preparations following pre-award requests (just-in-time (JIT)) will include submitting an initial IRB protocol. Startup will include hiring and training of study staff. Over the course of the study, preliminary and final results will be presented at appropriate scientific conferences (e.g., Research Society on Alcoholism, College on Problems of Drug Dependence, Research Society on Alcoholism, etc.).

Table 4. Study Timeline.

	Year 1													Year 2											
	Month													Month											
	1	2	3	4	5	6	7	8	9	10	11	12	1	2	3	4	5	6	7	8	9	10	11	12	
Pre-award prep																									
	Startup																								
				Phone screens: 250												IRB	NUL	BE	: H	C-N	S-1	-092			
				IRB APPROVAL												DAT	: 10	11/2							

			Intake evaluations: 100											
			Enrollment and randomization: 60 (~3-4 subjects/month)											
			Completion of protocol (~3-4 subjects/month)											

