			Data cleaning & analysis, write-up paper/grant renewal preparation											

PROTECTION OF HUMAN SUBJECTS

E.1. Risk to the Subjects

E.1.1. Human Subjects Involvement and Characteristics

The 2-year project will enroll male and female individuals (18 and older) regular alcohol users with past month excessive use of alcohol. Research data will be collected at screening, baseline, and weekly study visits.

This study is funded by the National Institute on Alcohol and Alcoholism (NIAAA). All studies funded by NIAAA, including this study, now submit data to the National Institute of Mental Health Data Archive (NDA) at the National Institutes of Health (NIH). All subject data will be de-identified by using a computer-generated global unique identifier (GUID) within the NDA database.

The single study site is the Center for Neurobehavioral Research on Addiction (CNRA) at the University of Texas McGovern Medical School, Houston. The CNRA is centrally located in a large U.S. metropolitan area known to have an adequate and representative alcohol-using population [see Facilities and Other Resources]. Moreover, the site has demonstrated its ability to recruit and retain the appropriate population using various recruitment strategies.

We plan on recruiting 4 participants/month over the course of 20 months for a total of 80 enrolled participants. We estimate that 60 participants (75%) will complete the study, based on previous studies from our group. Recruitment strategies will include local advertising in print media, public service announcements on radio, and referrals to CNRA in the Houston metropolitan area. Additionally, we will utilize the SONA system, which provides University of Houston students credit for participating in various research studies. Potential participants will complete a brief phone screen to assess initial eligibility and subsequently invited to undergo a comprehensive baseline screening following informed consent. The baseline screening will include a full medical evaluation by the CNRA Medical Director ([name]. Co-I). All participants will meet the following selection criteria.

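### The sample size is given as 60 enrolled for 50 completers in the design and timeline, but as 80 enrolled for 60 completers in the human-subjects section

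*Combined protocol and SAP*

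**What the plan says.** Two sets of figures appear in the current text.

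**Set A: 60 enrolled, 50 completers.**
- Approach, Participants: "We will enroll 60 participants to reach a target of" 50 completers, 25 per group.
- Study Timeline, text: "Our goal is to enroll 60 subjects to achieve 25 completers/group".
- Study Timeline, Table 4: "Enrollment and randomization: 60 (~3-4 subjects/month"), preceded by 250 phone screens and "Intake evaluations: 100".
- The power table (Table 3) uses 50 (25/25) and 40 (20/20). Sample Size and Power Considerations introduces these as "the different sample sizes (pragmatic and pessimistic) stipulated in" the table.

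**Set B: 80 enrolled, 60 completers.**
- Protection of Human Subjects, E.1.1: "We plan on recruiting 4 participants/month over the course of 20 months for a total of 80 enrolled participants". The next sentence reads: "We estimate that 60 participants (75%) will complete the study, based on previous studies from our group".

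The Study Timeline also leaves enrolment open: "However, we will continue to enroll subjects based on available resources and subject attrition". No number or upper limit is attached to that sentence, and nothing in the document links the two sets.

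**The concern.** The number enrolled and the number expected to complete are basic design figures, and here each has two values. Section E.1.1 also gives the only planning rate for completion, 75%, and that rate does not lead from 60 enrolled to 50 completers. The design sections therefore depend on a better rate that they neither state nor justify.

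Three things are at stake.
- **Exposure.** The enrolment number determines how many people receive study treatment, and the human-subjects section gives a figure one third higher than the design section (80/60 = 1.33).
- **Monitoring.** The Data Safety Monitoring Plan asks the board to evaluate recruitment and retention. With two totals and two rates it has no single benchmark: 45 completers out of 60 would meet the 75% expectation and miss the target of 50.
- **Power.** The more favourable row of Table 3 holds only if 50 complete.

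**Working it through.** **Inputs.** Set A: 60 enrolled, 50 completers (Participants; Study Timeline; Table 4). Set B: 4 per month, 20 months, 80 enrolled, 60 completers, 75% (E.1.1). Intake evaluations: 100 (Table 4). Power at N = 50 and N = 40 (Table 3).

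**1. Each set on its own.**
- Set B: 4 × 20 = 80 and 80 × 0.75 = 60. It reproduces exactly.
- Set A: 50/60 = 83.3% completion (dropout 1/6). This rate appears nowhere in the document.

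**2. One set's rate applied to the other's enrolment.**
- 60 × 0.75 = 45 completers, 22.5 per arm.
- 50/0.75 = 66.7, so 67 enrolled. For 25 in each arm, 25/0.75 = 33.3, so 34 per arm, or 68.
- 80 × 0.833 = about 67 completers, not 60.

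The sets differ by 20 enrolled, 10 completers and 8.3 percentage points of completion.

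**3. Whether 80 fits a stage of Table 4.** The stages are 250 phone screens, 100 intake evaluations and 60 enrolled and randomised. None is 80. Table 4 implies a yield of 60/100 = 60% from intake; 80 enrolled from the same 100 intakes would need 80%.

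**4. Chance of reaching the target.** The number of completers is taken as binomial, with participants completing independently and arms of equal size.

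| Enrolled | Completion rate | Expected completers | P(at least 50) | P(at least 25 in both arms) |
|---|---|---|---|---|
| 60 | 75% | 45 | 0.086 | 0.203² = 0.041 |
| 60 | 83.3% | 50 | 0.583 | 0.616² = 0.380 |
| 68 | 75% | 51 | 0.670 | 0.664² = 0.441 |
| 80 | 75% | 60 | 0.995 | 0.974² = 0.948 |

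For 60 enrolled at 75%, the central 95% range is 38 to 51 completers, and P(at least 40) = 0.946.

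**5. Power at 45 completers.** N = 45 lies midway between the two rows of Table 3.
- Aim 1, D = 0.30: (84.6 + 71.8)/2 = 78.2%, linear in N. Interpolating the probit of power on the square root of N gives 78.9%.
- Aim 2, 10% decrease: (90.8 + 74.6)/2 = 82.7%, linear. The probit version gives 84.2%.

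The Aim 1 entries come from 1000 simulations, with standard errors of about 1.1 to 1.4 points at D = 0.30, so whole points are as fine as these figures should be read: 78–79% and 83–84%.

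**The case against.** The best defence is that 60 is a goal and not a cap. The Study Timeline foresees further enrolment in response to attrition, which is the situation modelled above, and it describes its time frame as conservative. The accrual rates also overlap: 3 to 4 per month over 20 months gives 60 to 80. The 100 intake evaluations may themselves be conservative, so the 80% yield is weak evidence that E.1.1 is the passage out of date.

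Much of this stands. The 9% and 4% describe what happens if enrolment stops at 60 with 75% completing; they do not forecast the trial. They also need the benchmark in the second row of the table: even at 83.3%, 60 enrolled gives only a 58% chance of 50 completers and a 38% chance of 25 in both arms. Part of the low both-arms figure comes from requiring a minimum in each arm, and equal arms are an approximation under urn randomisation. The studies behind the 75% are not identified, so its relevance to this 8-week trial cannot be checked. The pessimistic N = 40 row already covers most of the likely shortfall, and the likelihood or imputation methods planned under Missingness & Multiple Comparisons may recover some information from non-completers.

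None of this reconciles the figures. The open-ended sentence gives neither 80 nor any maximum, and it does not explain why 50 complete in one place and 60 in another. Reading the 80 as consented and the 60 as randomised also fails, because E.1.1 describes the 80 as enrolled and the 60 as completing.

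**Conclusion.** The concern holds: the sample size is contradictory as written and must be corrected. This is an inconsistency between sections; the arithmetic within each is sound. The design, timeline and power table agree with one another, and E.1.1 is the exception on enrolment, although it is the only place that gives a basis for a completion rate. The document does not show which set is current.

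The case for correction rests on the conflicting figures and the unsupported 83.3%, not on a large loss of power. If 75% is right and enrolment stops at 60, the expected shortfall is 5 completers and power falls by roughly 6 to 8 points in the two least favourable effect-size columns of Table 3. That size depends on completer-based counting, independent completion and interpolation between two published rows. Table 3 is conditional on N and is not made wrong by this.

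**What to change.** State one enrolment number, one completion rate with its basis and one completer target, identically in Participants, the Study Timeline text, Table 4 and E.1.1. Add a maximum to the sentence that allows continued enrolment. The choice belongs to the sponsor:

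- **Keep 60 enrolled** and change E.1.1 to match. This is the cheapest route and adds no patients. Then do one of the following:
  - (a) State 45 expected completers at 75% and add an N = 45 row to Table 3, recalculated and not interpolated. The stated power becomes slightly less favourable.
  - (b) Keep 50 completers and add a sentence that states and justifies 83% completion.
- **Keep both 75% and 25 completers per group.** The consistent enrolment is 68 (34 per arm), 8 more than the 60-patient plan. The chance of 25 in both arms is then about 44%, because 68 meets the target only on average.
- **If 80 is the true plan**, change Participants, the Study Timeline text and Table 4 to 80 enrolled and 60 completers, 20 more patients than now shown there. Check the 100 intake evaluations and the accrual period as well: at 3 to 4 per month, 80 takes 20 to 27 months (80/4 to 80/3) in a 24-month project.
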